# 1. SYNOPSIS

Study Number	OPI-NYXP-301
Clinical Phase	Phase 3
Type of Study	Randomized, double-masked, placebo-controlled, multicenter study of the safety and efficacy of Nyxol ® (Phentolamine Ophthalmic Solution [POS] 0.75%) as a single agent and with adjunctive Pilocarpine Hydrochloride Ophthalmic Solution 0.4% (Low-Dose Pilocarpine, LDP) in subjects with presbyopia
Name of Investigational Products	Nyxol Eye Drops – POS 0.75% LDP 0.4%
Duration of Study	22 to 36 days
Study Objectives	

09/29/2023 Page 3 of 76

09/29/2023 Page 6 of 76

Subject Population	Approximately 320 randomized subjects with presbyopia
Inclusion Criteria	
 
Males or females ≥ 40 and ≤ 64 years of age.
 
Able to comply with all protocol-mandated procedures independently and to attend all scheduled office visits.
 
Able and willing to give signed informed consent.
 
Able to self-administer study medication throughout the study period.
 

	8.
Exclusion Criteria	Ophthalmic (in either eye):
	
 
Use of any topical prescription (including Vuity™) or over- the-counter (OTC) ophthalmic medications of any kind within 7 days of Screening until study completion, with the exception of lid scrubs with OTC products (eg, OCuSOFT® lid scrub, SteriLid®, baby shampoo, etc.) and artificial tears as specified in Exclusion #2 below.
 

	
 
Use of any OTC artificial tears (preserved or unpreserved) during Visit days or 15 min before or after instillation of Treatment 1 or Treatment 2.
 

	3. Current use of any dry eye product such as topical ophthalmic therapy for dry eye (eg, generic cyclosporine, Restasis, Xiidra, Cequa, and Eysuvis) or intranasal dry eye product (eg, Tyrvaya) or other devices.
	4. Tear break-up time of < 5 seconds or corneal fluorescein staining Grade $\geq 2$ in the inferior zone or Grade $\geq 1$ in the central zone using the National Eye Institute scale.
	
 
Clinically significant ocular disease (eg, cataract, glaucoma, corneal edema, uveitis, retinal degeneration, loss of visual field, or any macular pathology) that might interfere with the study as deemed by the Investigator.
 

	
 
Recent or current evidence of ocular infection or inflammation in either eye (such as current evidence of clinically significant blepharitis, conjunctivitis, keratitis, etc.). Subjects must be symptom free for at least 7 days.
 

,	7. Any history of herpes simplex or herpes zoster keratitis.
8	8. Known allergy, hypersensitivity, or contraindication to any component of the phentolamine, pilocarpine, or vehicle formulations.
9	
 
Prior participation in a study involving the use of Nyxol for the treatment of presbyopia.
 

	0. History of cauterization of the punctum or punctal plug (silicone or collagen) insertion or removal.
	1. Ocular trauma within 6 months prior to Screening.
	2. Ocular surgery or any ocular laser treatment within 6 months prior to Screening.
	3. Subjects with surgical monovision, multifocal or extended depth of focus intraocular lenses (IOLs) are excluded (monofocal IOLs are accepted if in place > 6 months prior to Screening).
	4. History of any traumatic (surgical or nonsurgical) or nontraumatic condition affecting the pupil or iris (eg, irregularly shaped pupil, neurogenic pupil disorder, iris atrophy, iridotomy, iridectomy, iritis, etc.).
	5. Contact lens wear on the day of any study visit and contact lenses must be removed for home dosing and for at least 10 minutes following dosing.
	Systemic:
	
 
6. Known hypersensitivity or contraindication to alpha- and/or beta-adrenoceptor antagonists (eg, chronic obstructive pulmonary disease or bronchial asthma; abnormally low blood pressure [BP] or heart rate [HR]; second- or third-degree heart blockage or congestive heart failure).
 

	7. Known hypersensitivity or contraindication to any systemic cholinergic parasympathomimetic agent.
	18. Clinically significant systemic disease (eg, uncontrolled diabetes, myasthenia gravis, cancer, hepatic, renal, endocrine, or cardiovascular disorders) that might interfere with the study as deemed by the judgment of the Investigator.
	9. Initiation of treatment with, or any changes to, the current dosage, drug, or regimen of any systemic adrenergic or cholinergic drugs within 7 days prior to Screening or during

	the study; however, Flomax (tamsulosin) is specifically excluded.
	20. Participation in any investigational study within 30 days prior to Screening.
	21. Females of childbearing potential who are pregnant, nursing, planning a pregnancy, or not using a medically acceptable form of birth control. Acceptable methods include the use of at least one of the following: intrauterine device (IUD), hormonal (oral, injection, patch, implant, ring), barrier with spermicide (condom, diaphragm), or abstinence. A female is considered to be of childbearing potential unless she is 1 year postmenopausal or 3 months post-surgical sterilization. All females of childbearing potential, including those with post-tubal ligation, must have a negative urine pregnancy test result at Visit 1 (Screening/Baseline).
	
 
22. Resting HR outside the range of 50 to 110 beats per min following at least a 5-min rest period in the sitting position at Visit 1 (Screening/Baseline). Heart rate may be repeated only once if outside the specified range, following another 5-min rest period in the sitting position.
 

	
 
23. Hypertension with resting diastolic BP > 105 mmHg or systolic BP > 160 mmHg following at least a 5-min rest period in the sitting position at Visit 1 (Screening/Baseline). Blood pressure may be repeated only once if outside the specified range, following another 5-min rest period in the sitting position.
 

Study Assessments	BCDVA
	Distance-corrected intermediate visual acuity (DCIVA)
	DCNVA
	PD Biomicroscopy
	Intraocular pressure (IOP)
	Direct or indirect ophthalmoscopy without dilation
	Urine pregnancy test for females of childbearing potential
	HR and BP
	Ocular tolerability
	Subject questionnaire
	Corneal fluorescein staining (for eligibility only)

Number of Investigational Sites	Approximately 30 sites
Estimated Total Sample Size	Approximately 320 randomized subjects
Sample Size Justification	Using $\alpha = 0.05$ significance and a two-tailed test, 300 total subjects (150 subjects each in the Nyxol and placebo arms) who are evaluable for efficacy in percent of subjects with $\geq 15$ letters of improvement in photopic binocular DCNVA and with < 5 letters of loss in photopic binocular BCDVA from Baseline at 12 hours post-dose at Visit 2 (Stage 1 Day 8). This calculation is based on . An additional 20 subjects will be enrolled to account for dropouts.
Primary Efficacy Endpoint	The primary efficacy endpoint is the percent of subjects with $\geq 15$ letters of improvement in photopic binocular DCNVA and with < 5 letters of loss in photopic binocular BCDVA at 30 min post-LDP/vehicle comparing Nyxol + LDP to placebo + LDP vehicle at Visit 5 (Stage 2 Day 8). This comparison will be analyzed first using a hierarchical testing method.
Key Secondary Efficacy Endpoints	
Other Secondary Efficacy Endpoints	

09/29/2023 Page 11 of 76

	All efficacy endpoints will be analyzed overall and by light/dark irides. Separate analyses will be performed for binocular, study eye, and fellow eye, where applicable. All efficacy endpoints will also be analyzed by the Modified Intention-to-Treat (mITT) Population. Selected analyses will be performed on the Per Protocol (PP) Population as specified in the Statistical Analysis Plan (SAP).
Safety Endpoints	Safety measures are adverse events, ocular tolerability, IOP, BCDVA, biomicroscopy, ophthalmoscopy, HR and BP, and subject questionnaire. Urine pregnancy tests for females of childbearing potential will be conducted.
Study Medications, Dose, and Mode of Administration	Treatment 1:         • Nyxol ® Eye Drops (Phentolamine Ophthalmic Solution 0.75%), or         • Placebo (ie, Nyxol vehicle)         Treatment 1 is dosed during both Stages 1 and 2 of the study and is taken daily in the evenings near bedtime, except during the Washout Period.         Treatment 2:         • LDP (Pilocarpine Hydrochloride Ophthalmic Solution 0.4%), or         • LDP vehicle         Treatment 2 is dosed during Stage 2 of the study and is taken daily in the mornings.

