# Efficacy Results From the VEGA-1 Study:

#### Nyxol as a Single Agent

Following 3 to 4 days of treatment with Nyxol or placebo, 30.1% of Nyxol-treated subjects had  $\geq 15$  letters of improvement in photopic binocular DCNVA compared with 13.5% of placebo-treated subjects 12 hours after the last dose (p=0.0265). This benefit remained stable over the next 6 hours, with a mean of 36.7% of Nyxol-treated subjects improving by 15 or more letters DCNVA 18 hours post-dose

Significantly more subjects treated with Nyxol achieved binocular DCNVA of 20/40 or better compared with placebo (56% vs 36%, respectively; p=0.0080).

Photopic binocular mean DCNVA showed significantly greater improvement in mean number of letters read among Nyxol-treated subjects (10.1-letter improvement) compared with placebo-treated subjects (5.6-letter improvement) at 12 hours post-dose (p=0.0006). Consistent with these results, mean photopic PD in the best eye was significantly reduced among Nyxol-treated subjects compared with placebo-treated subjects at 12 hours post-dose (p<0.0001).

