# *Nyxol* + *LDP* as *Adjunctive Therapy*

A statistically significantly greater number of subjects in the Per Protocol (PP) Population treated with Nyxol + LDP had  $\geq$  15 letters of improvement in photopic binocular DCNVA at 1 hour post-LDP treatment (primary endpoint) compared with placebo alone (60.45% vs 27.9%, respectively; p=0.0037). In addition, the Nyxol + LDP arm had significantly more subjects with  $\geq$  15 letters of improvement in photopic binocular DCNVA compared with placebo alone at all timepoints from 30 min through 4 hours post-LDP treatment ( $p\leq$ 0.0166 for each). This benefit was retained for all timepoints between 30 min and 4 hours when requiring that subjects with  $\geq$  15 letters of improvement in photopic binocular DCNVA also had to have < 5 letters of loss in photopic binocular best-corrected distance visual acuity (BCDVA), the accepted registration endpoint. The benefit of LDP adjunctive therapy to Nyxol was consistent regardless of iris color.

The effect of Nyxol + LDP on DCNVA was rapid and clinically significant. By 30 min post-LDP treatment, 79% of subjects had photopic binocular DCNVA of 20/40 or better. By 1 hour post-LDP

treatment, 84% of subjects had binocular DCNVA of 20/40 or better. Significantly more subjects treated with LDP adjunctive to Nyxol had photopic binocular DCNVA 20/40 or better compared with placebo at 30 min through 2 hours ( $p \le 0.0119$  for each).

Nyxol + LDP treatment resulted in more subjects achieving a  $\geq$  15-letter improvement in DCNVA compared with each of its components used individually at all timepoints from 30 min to 2 hours post-LDP treatment. Although the study was not statistically powered for this outcome, the percent of responders at 30 min with combination therapy (61%) was significantly greater than the response rate with LDP alone (26%; *p*=0.0076) or Nyxol alone (33%; *p*=0.0265).

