#### 3.5. Study Population

The study population for this trial will be comprised of males and females between 40 and 64 years of age with presbyopia. A sample size of approximately 320 subjects will be randomized into 1 of

4 treatment arms, with the expectation that approximately 300 subjects will be evaluable for efficacy.

- Nyxol + LDP
- Nyxol + LDP vehicle
- Placebo (ie, Nyxol vehicle) + LDP
- Placebo + LDP vehicle

Subjects will be randomized 1:1:1:1 into the above groups.

At Visit 1 (Screening/Baseline), eligible subjects will be randomized, and the first dose of Treatment 1 will be administered (note: if Visit 1 is split into 2 separate days, then dosing occurs on the second day). Efficacy and safety measurements are made before dosing with Treatment 1 (Time 0 min) and at multiple post-dose timepoints from 30 min to 8 hours. If Visit 1 is split over 2 separate days, all Screening assessments up to and including randomization must occur on the first day, and then the subject should return to complete their post-randomization assessments in the following order on the second day (ie, confirm concomitant medications, subject questionnaire, in-office Treatment 1 dosing, ocular tolerability, followed by all other assessments at time points 0.5, 1, 3, 5, and 8 hours post-treatment). Prior to discharge following completion of Visit 1 (Stage 1 Day 1), Treatment 1 study medication for Stages 1 and 2 will be dispensed for evening dosing by the subject before bedtime, to begin the night of Stage 1 Day 2. On the evening prior to Visit 2, the subject will dose Treatment 1 study medication as close to 12 hours prior to Time 0 min for that visit.

At Visit 2 (Stage 1 Day 8), efficacy and safety measurements will be made at 12 hours after the dose of Treatment 1 study medication (12-hour endpoint). After completion of these assessments, **the subject will take no study drug for 7 to 14 days (during the Washout Period)**, after which Stage 1 is complete. Measurements will be made on Visit 3 (Stage 1 Day  $10 \pm 1$  day) during the Washout Period to assess the absence of residual treatment effects.

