# 5. STUDY DESIGN

This is a randomized, double-masked, placebo-controlled, multicenter, Phase 3 study in approximately 320 subjects with presbyopia. The study will be performed in 2 stages, as shown in Appendix 4.

Subjects will be randomized 1:1:1:1 to treatments for both stages at Visit 1 (Screening/Baseline). Treatment 1 assignment in Stage 1 will be maintained for Stage 2. Stage 1 will consist of 2 treatment groups (Nyxol or placebo [ie, Nyxol vehicle]), with approximately 160 subjects in each group. Stage 2 consists of 4 treatment groups (Nyxol + LDP, Nyxol + LDP vehicle, placebo + LDP, and placebo + LDP vehicle), with approximately 80 subjects per treatment group.

In Stage 1, the safety and efficacy of Nyxol as a single agent will be evaluated over the following 1 day and 7 days of daily dosing in the evenings near bedtime, except the evening before Visit 2, when Treatment 1 is dosed as close to 12 hours prior to Time 0 min for that visit. Following Visit 2 (Stage 1 Day 8), subjects will discontinue dosing Treatment 1 for 7 to 14 days (Washout Period). During the Washout Period, subjects will return for Visit 3 (Stage 1 Day  $10 \pm 1$  day) to assess the resolution of drug treatment effects.

During Stage 1, subjects will dose with Treatment 1 (Nyxol or placebo [ie, Nyxol vehicle]) in the evenings near bedtime (except for Visit 1 [Stage 1 Day 1], when the subject is dosed during the day at the study site).

Measurements will be made at multiple visits and timepoints, and analysis will consist of comparison across the 2 arms:

- Nyxol
- Placebo

# Stage 2: Dosing of Treatments 1 and 2

Visit 4 (Stage 2 Day 1) is the start of Stage 2. In Stage 2, the efficacy and safety of Nyxol + LDP will be evaluated following 1 day and 7 days of dosing, in which Treatment 1 (Nyxol or placebo) is dosed daily in the evenings near bedtime, except the evening before Visits 4 and 5, when Treatment 1 is dosed as close to 12 hours prior to the scheduled time for those visits. Treatment 2 (LDP or LDP vehicle) is dosed daily in the mornings. Treatment 2 will be dosed at the study site at the beginning of Visits 4 and 5 (Stage 2 Days 1 and 8, respectively).

Measurements will be made at multiple visits and timepoints, and analysis will consist of comparison across the 4 arms:

- Nyxol + LDP
- Nyxol + LDP vehicle
- Placebo + LDP
- Placebo + LDP vehicle

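### Does a Synopsis sample size row written for the Visit 2 comparison leave the Visit 5 primary without a sound basis for its size?

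*Protocol*

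**What the plan says.** The Synopsis row on sample size uses a two-sided 5% test and gives "300 total subjects (150 subjects each in the Nyxol and placebo arms) who are evaluable for efficacy". It ties that number to the composite responder endpoint "from Baseline at 12 hours post-dose at Visit 2 (Stage 1 Day 8"). The sentence that should give the assumed rates is blank. Twenty subjects are added for dropouts, making about 320.

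The next Synopsis row defines the primary endpoint as the same composite at 30 min after Treatment 2, "comparing Nyxol + LDP to placebo + LDP vehicle at Visit 5 (Stage 2 Day 8"). Protocol 5.1, 8.1 and 10.3.5 and SAP 4.2.1 agree.

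Protocol 5 and SAP 5.1 describe two groups of about 160 in Stage 1 and four groups in Stage 2, "with approximately 80 subjects per treatment group". Protocol 3.5 randomises about 320 "with the expectation that approximately 300 subjects will be evaluable for efficacy", without naming a visit. The readable part of Protocol 10.1 gives only the allocation and the 20 extra subjects. SAP 6 is redacted.

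**The concern.** Justification and primary endpoint stand one above the other in the Synopsis and describe different tests. The justification concerns Nyxol against placebo, 150 per arm, 12 hours, Visit 2. The primary concerns the combination against double vehicle, about 80 per arm, 30 min, Visit 5. A reader could take the 150, and whatever power was attached to it, as the basis of the confirmatory test, which has roughly half that number in each arm.

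If the primary had simply inherited a number worked out for another contrast, the confirmatory test might be too small without anyone having checked. The single-agent effect shows the risk: a calculation that is comfortable at 150 per arm is not comfortable at 80 per arm for the same effect.

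**Working it through.** **Inputs.** Two-sided alpha 0.05 (Synopsis). Randomised 320, evaluable 300, allocation 1:1:1:1 (Synopsis; Protocol 3.5, 10.1). The planning rates are unreadable, so the VEGA-1 rates in Protocol 3.2 are used as assumptions:
- Nyxol 30.1% and placebo 13.5% at 12 hours.
- Nyxol + LDP and placebo at 1 hour, per protocol: "60.45% vs 27.9%, respectively; p=0.0037".
- Nyxol + LDP at 30 min: 61%.

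All of these are for near-vision gain alone. Protocol 3.2 says the benefit held when the distance-vision condition was added, but gives no composite rates.

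**Counts.** 300 + 20 = 320, and 20/320 = 6.25%. Stage 1: 320/2 = 160 randomised and 300/2 = 150 evaluable per arm, as stated. Stage 2: 320/4 = 80 randomised per arm. A figure of 300/4 = 75 needs two assumptions, that the 300 applies at Visit 5 and that it splits evenly. The documents give neither. The primary analysis uses the mITT population, which is everyone randomised with at least one drop of Treatment 1, with imputation of missing primary data (Protocol 10.2, 10.3.5; SAP 7.1.1, 9). Its size is therefore close to 80 per arm. The value 75 serves below as a low reference.

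**Formula.** With d = p1 − p2 and p̄ the mean of the two rates,

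power = Φ{[d√n − 1.96√(2p̄(1−p̄))] / √(p1(1−p1) + p2(1−p2))}.

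**Visit 2 figure.** It cannot be strictly reproduced, because its rates and power are unreadable. With 30.1% and 13.5%: d = 0.166, p̄ = 0.218, 1.96√(2 × 0.218 × 0.782) = 1.144, denominator √(0.2104 + 0.1168) = 0.572.
- n = 150: (2.033 − 1.144)/0.572 = 1.55, power 94.0%.
- n = 80: (1.485 − 1.144)/0.572 = 0.59, power 72.4%.
- n = 75: power 69.6%.
- 90% power needs 128 per arm and 95% needs 158, so 150 is plausible for this comparison but not confirmed.

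**Visit 5 primary.** With 60.45% and 27.9%: d = 0.3255, p̄ = 0.44175, 1.96√(2 × 0.44175 × 0.55825) = 1.376, denominator √(0.2391 + 0.2012) = 0.6635.
- n = 80: (2.911 − 1.376)/0.6635 = 2.31, power 99.0%.
- n = 75: (2.819 − 1.376)/0.6635 = 2.17, power 98.5%.
- 90% power needs 47 per arm.
- With 61% against the same 27.9% (a 30 min rate paired with a 1 hour rate): 99.2% at 80, 98.8% at 75, and 46 per arm for 90%.

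**Range at 80 per arm**

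| True difference | Control 13.5% | Control 27.9% |
|---|---|---|
| 20 points | 85.4% | 74.6% |
| 25 points | 95.7% | 90.4% |
| 30 points | 99.1% | 97.5% |

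The difference detectable with 80% power is 18.5 points (control 13.5%) to 21.5 points (control 27.9%). The VEGA-1 difference was 32.55 points, and 21.5/32.55 = 0.66. The effect could therefore shrink by about a third before power reached 80%.

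**Which comparison asks for more subjects?** For 90% power on these rates, Visit 2 needs 2 × 128 = 256 evaluable in all. The Visit 5 primary needs 4 × 47 = 188 across four equal arms. A trial sized on the Visit 2 comparison would more than cover the Visit 5 primary.

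**The case for a change.** The best case for acting is that both rows are current text, so the mismatch is not left over from the amendment log. SAP 7.3.2 also still describes the primary endpoint as the Visit 2, 12-hour comparison, which suggests that the Synopsis row was not revisited when the primary moved. Whatever lies under the redactions, the readable words fix the arms, visit and timepoint of the stated calculation, and they are not those of the primary. A reader is entitled to see the basis for the confirmatory test, particularly as power depends on the effect assumed: a 20-point difference gives only 74.6% to 85.4% at 80 per arm. One label and one sentence would settle it.

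Part of this stands. The row describes a different comparison from the primary and does not say so, and the single-agent power at 150 per arm does not carry over to 80.

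The rest does not establish a fault. The readable row never claims to size the primary test. It describes a comparison that the plan still makes (Protocol 5; SAP 5.1, 9.1.2), so nothing in it is untrue. A Visit 5 calculation may sit in the gap in that very row, in Protocol 10.1 or in SAP 6, and blacked-out text cannot be counted as absent. Nor do the documents allow a firmer statement in the other direction. With the planning inputs unreadable, nobody can say that 150 is the right size for Visit 2 or that it was the original basis for the total. No passage gives an evaluable count at Visit 5, so writing 75 into the Synopsis would introduce an unsupported number.

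**Conclusion.** The mismatch is real but clerical. The row's 150 per arm is consistent with the Stage 1 allocation, and the primary's roughly 80 per arm can be read directly from Protocol 5 and SAP 5.1. No shortfall is shown. Power for the primary is about 99% at 80 per arm if the VEGA-1 effect holds, and at least 90% at 25 points for control rates from 13.5% to 27.9%. A label on the row would make it easier to read, but would leave the sample size, alpha, analysis, result and conclusion as they are. No change to the plan follows.

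This rests on VEGA-1 rates standing in for the hidden planning rates. Those rates omit the distance-vision condition, and the control rate is at 1 hour rather than 30 min. It also rests on the mITT analysis keeping nearly all of those randomised. The conclusion would differ only if the unredacted text gave no basis for the Visit 5 primary and the true difference were near 20 points or less. The documents show neither.

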# 2. ABBREVIATIONS AND TERMS

Abbreviation	Full term
AE	adverse event
ANCOVA	analysis of covariance
ARP	All Randomized Population
BCDVA	best-corrected distance visual acuity
BP	blood pressure
cGMP	current Good Manufacturing Practice
CI	confidence interval
CRA	clinical research associate
CRO	contract research organization
DCNVA	distance-corrected near visual acuity
eCRF	electronic Case Report Form
ETDRS	Early Treatment Diabetic Retinopathy Study
FDA	Food and Drug Administration
GCP	Good Clinical Practice
HR	heart rate
IB	Investigators' Brochure
ICH	International Council for Harmonisation
IOL	intraocular lens
IOP	intraocular pressure
IRB	Institutional Review Board
ITT	Intention-to-Treat
IUD	intrauterine device
LDP	Low-Dose Pilocarpine Hydrochloride Ophthalmic Solution 0.4%; Low-Dose Pilocarpine
LDPE	low-density polyethylene
LSM	least-squares mean
MedDRA	Medical Dictionary for Regulatory Activities

mITT	Modified Intention-to-Treat
Nyxol	Phentolamine Ophthalmic Solution 0.75%
Nyxol + LDP	Nyxol dosed in the evenings with LDP dosed during the mornings
OD	oculus dexter (right eye)
OR	odds ratio
OS	oculus sinister (left eye)
OTC	over-the-counter
OU	oculus uterque (both eyes)
РСН	pilocarpine hydrochloride
PD	pupil diameter
POS	Phentolamine Ophthalmic Solution
PP	Per Protocol
PPS1	PP Protocol Population Stage 1
PPS2	PP Population Stage 2
SAE	serious adverse event
SAP	Statistical Analysis Plan
SOC	system organ class
SP	Safety Population
TEAE	treatment-emergent adverse event
US	United States
USP	United States Pharmacopeia
VA	visual acuity

